### **1.0 BACKGROUND AND RATIONALE**

#### 1.1 Study Synopsis

This is an investigator-initiated, prospective study designed to evaluate the accuracy of contrast-enhanced ultrasound (CEUS) with microbubble contrast agent (perflutren lipid; Definity®) to identify malignancy in patients with kidney disease, a known risk factor for kidney malignancy, in whom a conventional ultrasound (US) shows an indeterminate cystic kidney lesion.

The primary objective of the study is to estimate the sensitivity of CEUS in diagnosing kidney malignancy in patients with a risk factor for kidney malignancy and compare it to the current gold standard test in this patient population. Secondary analysis will include more optimal contrast-enhanced imaging with computed tomography (CT) or magnetic resonance imaging (MRI) in a subset of patients who can receive these studies. The study outcome will lead to immediate clinical application in patients with chronic kidney disease. Given the costeffectiveness and adverse event profile, it has excellent potential to become established as first line diagnostics in the general patient population as well.

#### 1.2 Background

#### Introduction

According to the US Renal Data System 2014 report, there are over 600,000 people in the US living with end stage kidney disease (ESKD) with almost 450,000 receiving dialysis. In a large collaborative international study, kidney cancers have a standardized incidence ratio of 3.6 in patients receiving dialysis meaning that for the nearly 500,000 patients receiving dialysis, there are an additional 50,000 cases of kidney cancer that occur above that of the general population. More recent findings show that patients with chronic kidney disease (CKD) are also at increased risk of kidney cancer, with hazard ratios increasing with CKD stage. For this reason, patients on the waiting list for renal transplant and those receiving dialysis have been advised to have annual screenings for kidney malignancy.

Currently, contrast-enhanced CT and MRI are the gold standard imaging studies for kidney lesion characterization. However iodinated contrast agents are nephrotoxic in patients with renal insufficiency and therefore contraindicated in patients with a serum creatinine > 2.0 as they can lead to permanent deterioration of kidney function. Until recently, contrast MRI was a suitable alternative. However, Nephrogenic Systemic Fibrosis (NSF) is now regarded as a serious, potentially lethal complication of the gadolinium contrast agents used in MRI if administered to patients with impaired renal function. Inadequate preoperative imaging can lead to unnecessary nephrectomy, which would further limit already compromised renal function. There is therefore a need for an imaging method for evaluating renal masses that does not use iodinated or gadolinium contrast agents. CEUS represents one potential alternative.

#### Contrast-Enhanced US Diagnostic Imaging of the Kidney

For CKD patients screened annually for kidney malignancy, US imaging of the kidney is performed in the United States without contrast as no US contrast agent is approved for this indication. Without contrast, malignant tumors cannot be differentiated from benign tumors or pseudotumors. Typically, following the identification of a kidney lesion via US without contrast, contrasted-CT or MRI may then be performed to stage and grade the lesion, depending on a risk/benefit analysis performed by the patient's physician. If a contrasted-CT or MRI is deemed too risky, the patient may proceed directly to surgery, or more likely, will be followed closely with repeated non-contrast imaging, typically anywhere from 1-5 years.

US contrast agents are gas-filled microbubbles which are intravenously administered in very small volume boluses or slow infusions. These microbubbles typically have mean diameters between 1 to 6  $\mu$ m^5, remain intravascular for several minutes, and do not diffuse into the interstitium (pure blood-pool agents). The first generation of microbubbles was air encapsulated in albumin (Albunex®) or in lipid/galactose polymers (Levovist®). These microbubbles were hampered by the relatively fast outward diffusion of air, decreasing the gas volume and thereby reducing the contrast enhancement. The following generation used inert high molecular weight gases with low diffusion coefficients and low solubility in water such as perfluorocarbon gases or sulfur hexafluoride encapsulated in lipid, protein or polymer shells.

Early microbubble studies were performed with Doppler-based imaging methods which rely on the detection and quantification of shifts in the frequency of the received US signals. This method was hampered by an inability to assess microvascular blood flow. Later, advances in US imaging utilized the detection of harmonic frequencies produced by microbubbles, thereby allowing for more sensitive detection of microbubbles and improving imaging of tissue microvasculature. Further improvements in harmonic imaging and the discovery of the nonlinear properties of microbubbles have spurred the development of contrast-specific US techniques such as CPS (Contrast Pulse Sequencing). Such imaging techniques provide high-resolution images of tissue vasculature and allow the assessment of the microcirculation patterns in real-time. Outside of the United States, or in the context of clinical trials, US contrast agents have been used in kidney imaging. Levovist® (lipid and galactose microparticle suspension) and Sonovue® (lyophilized sulfur hexafluoride microbubbles), two non-FDA approved similar US contrast agents approved for use in countries outside of the United States, have been used in the general population to identify and diagnose renal pseudotumors, cystic renal lesions and solid renal lesions. See a descriptive table of these studies below. To date, no study

#### CONFIDENTIAL UNIVERSITY OF NORTH CAROLINA

has evaluated the effectiveness of any US contrast agents in patients with renal	
insufficiency who are at an increased risk for both cystic and solid renal lesions.	

Author	Contrast	Imaging	#	Lesion	Degulta		
(year)	Agent	Method	lesions	Туре	Kesuits		
Kim (1999) 	Levovist ®	Power Doppler	13	Cystic	PPV: 100% NPV: 57% DxA: 77%		
Ascenti (2001) 	Levovist ®	Power Doppler	41	Solid	DxA: 78%		
Ascenti (2004) 	SonoVue®	2 nd Harmonic	40	Solid	"Se: 85.7%		
Park (2005) 	Levovist ®	2 nd Harmonic	30	Solid	Se: 97% Sp: 93% DxA: 95%		
Tamai (2005) 	Levovist ®	SieFlow	29	Solid	Se: 94.4% Sp: 45.4% PPV: 100%		
Wink (2007) 	SonoVue®	CPS	20	Solid & Cystic	Se: 95%		
Quaia (2008) 	SonoVue®	CPS	40	Cystic	Se: 89% Sp: 73.6% PPV: 79.3% NPV: 86% DxA: 82%		
Fan (2008) 	SonoVue®	CPS	72	Solid	Sp: 96.4% Se: 77.3%		
Meloni (2008) 	SonoVue®	CPS	30	Solid	Se: 96.6% Sp: 100% PPV: 100% NPV: 95.8% DxA: 98.1%		
Roy (2008) 	SonoVue®	CPS	86	Solid & Cystic	Sp: 55992.9% - Papillary carcinoma 57.1% - Clear Cell carcinoma 100% - Oncocytoma 100% - Benign		
Abbreviations: PPV – Positive Predictive Value, NPV – Negative Predictive Value, DxA –							
Diagnostic Accuracy, Se – Sensitivity, Sp – Specificity							

In the United States, where there has been significantly less research on using US contrast in humans, the US contrast agent, Definity®, has recently been used in one study to measure renal blood flow in a healthy population, effectively reproducing previous animal studies in the human population. Only two US contrast agents are FDA approved for human use: perflutren lipid microspheres (Definity®) and perflutren protein-type A microspheres (Optison®). These agents differ in that perflutren lipid (Definity®) has a lipid coat and Optison® an albumin coat. Both are FDA indicated only for use in cardiac studies.

#### 1.3 Perflutren Lipid Background and Associated Known Toxicities

See http://www.accessdata.fda.gov/scripts/cder/drugsatfda/ for full prescribing information on perflutren when used according to its FDA-approved indication. Also

#### CONFIDENTIAL UNIVERSITY OF NORTH CAROLINA

see section 5.7.

#### 1.3.1 Background

Definity® (perflutren lipid) is an FDA-approved US contrast agent indicated to opacify the left ventricular chamber and to improve the delineation of the left ventricular endocardial border in patients with sub-optimal echocardiograms. It is activated by mechanical agitation with a Vialmix® which produces a milky white injectable suspension of perflutren lipid microspheres composed of octafluoropropane. Activated perflutren may be injected by either an intravenous bolus or infusion. See http://www.accessdata.fda.gov/scripts/cder/drugsatfda/ for full prescribing information when used in this indication. When used in this setting, the maximum dose of perflutren is administered as either two bolus doses or one single intravenous infusion.

#### **1.3.2 Associated Toxicities**

In pre-market clinical trials, 1716 subjects were evaluated with activated perflutren lipid. Of the 1716 subjects, 144 (8.4%) had at least one treatment-related adverse reaction. There were 26 serious adverse events and 15 (0.9%) subjects discontinued because of an adverse event. Nineteen subjects (1.1%) suffered serious cardiopulmonary adverse events including 8 deaths. The deaths occurred several days after activated perflutren lipid administration and appear to be related to the course of underlying disease. Of the 11 other serious adverse events, which appeared within 2-15 days of the drug administration, all appeared to be a progression of underlying cardiac and non-cardiac disease. However, a role for perflutren lipid in the initiation or course of these adverse events cannot be ruled out.

There were 15 discontinuations reported. Nine of these patients were discontinued after the first injection. One patient experienced a hypersensitivity reaction with urticaria and pruritus and all the other patients experienced dizziness, chest pain, dyspnea or back pain. Adverse events (AEs) appeared within 1 – 15 minutes of the drug administration and were of moderate intensity resolving usually without treatment within minutes or hours after onset.

For all AEs, there were no differences in the overall incidence based on age, gender, or route of administration. The most common events were (% of patients experiencing): headache (2.3%), back and renal pain (1.2%), flushing (1.1%) and nausea (1.0%).

#### **Cardiopulmonary Reactions**

In 2007, in response to post-marketing reports of 4 deaths and 190 serious cardiopulmonary reactions, the FDA issued a black box warning for both Definity® and Optison® adding disease state contraindications and a mandatory 30 minute monitoring period following administration in all patients. Following this there have been several large-scale safety studies looking into the records of a total of more

# CONFIDENTIAL UNIVERSITY OF NORTH CAROLINA

than 200,000 patients who received one of these contrast agents. In all those studies a composite rate of serious adverse events was calculated to be 1 - 3 in 10,000, compared to gadolinium-based MRI contrast which has an incidence of NSF of 2 - 5 in 100 patients with chronic kidney disease.

Following a meeting of the FDA Cardio-renal Advisory Committee in 2008, the black box warning was revised. The revisions shortened the contraindications to include cardiac shunts and hypersensitivity to perflutren and mandated the 30-minute monitoring period be limited to patients with pulmonary hypertension or unstable cardiopulmonary conditions. The black box warning was further revised in 2011, removing the mandatory 30-minute monitoring period, but stating that most serious cardiopulmonary reactions occur within 30 minutes of administration. For this reason, the label states that cardiopulmonary resuscitation personnel and equipment be readily available prior to perflutren administration, and that all patients be monitored for acute reactions.

Patients with a history of cardiac shunts, pulmonary hypertension or unstable cardiopulmonary conditions will be excluded from our study. In addition, all patients will be monitored for 30-minute post-perflutren administration by the research or clinical nurse or research physician.

#### Hypersensitivity Reactions

The real risk of perflutren in our study is to the small number of potential patients with an undiagnosed allergy to perflutren. Post-marketing reports have included anaphylactoid events and other serious but non-fatal adverse reactions, typically within 30 minutes of drug administration (see the package insert, and section 5.7 for additional information. In order to avoid a potentially fatal event, EpiPen® (epinephrine) injections will be kept near the US machine for all patients.

#### High Ultrasound Mechanical Index (MI)

High ultrasound MI values may cause microsphere cavitation or rupture and lead to ventricular arrhythmias. In addition, end-systolic triggering with high MI has been reported to cause ventricular arrhythmias. While the safety of perflutren at MIs >0.8 has not been established by the manufacturer, real-time measurement of renal blood flow in 19 healthy subjects using perflutren was recently reported, using a flash replenishment high-MI (MI of 1.0) US technique. The contrast agent was well tolerated with no serious adverse events. One patient each had a 20 mmHg increase in systolic blood pressure, a very brief and mild episode of flushing, and mild back pain, but no cardiac arrhythmias were recorded during the study period.

A second study using the Sonovue® contrast agent with flash-replenishment high-MI to detect changes in kidney perfusion via US in 10 normal volunteers reported the agent was well tolerated, and not associated with any adverse events. The safety of using a flash-replenishment high MI echocardiography with Sonovue®

#### CONFIDENTIAL UNIVERSITY OF NORTH CAROLINA

has been established in patients with chest pain of undetermined origin as well as in patients undergoing stress testing for detection of ischemia.

#### Use in Renal Insufficiency

US contrast agents including perflutren should carry no additional risks in patients with renal insufficiency, as peflutren is cleared by the lungs. The phospholipid component of perflutren lipid microspheres is thought to be metabolized to free fatty acids, while the octafluoropropane (OFP), as a stable gas, is not metabolized. In a small (n=8) pharmacokinetic study in healthy subjects, OFP was undetectable after 10 minutes in most subjects either in the blood or expired air, with a mean half-life of 1.3 minutes (Definity® Prescribing Information).

The UNC Division of Cardiology routinely uses perflutren as an echocardiographic contrast agent, including in patients with renal insufficiency.

#### 1.4 Rationale

At this time, contrast-enhanced CT and MRI are the standard imaging studies for evaluation of suspected renal tumors. However, there are serious adverse effects from iodinated CT contrast and gadolinium MRI contrast in patients with renal insufficiency. Currently, to reduce exposure of potentially nephrotoxic contrast agents in patients with renal insufficiency, use of iodinated CT and gadolinium MR is limited to those patients in whom US without contrast indicates a suspicious or indeterminate lesion, and for whom the risk/benefit ratio warrants this risk.

Our primary objective is to compare the accuracy of perflutren enhanced US to the current clinical gold standard of follow-up non-contrasted imaging in patients with CKD. The accuracy of perflutren-enhanced US will be determined by comparing results of the perflutren-enhanced US with the Truth Standard (change in 1-year follow-up non-contrast US imaging). In patients where tissue diagnosis or contrasted imaging (CT or MRI) is available, these results will be incorporated into the Truth Standard in a secondary analysis.

Unlike CT and MRI contrast agents, US contrast agents are not associated with complications in patients with impaired kidney function. We hope to show that contrast-enhanced US may provide a viable alternative to contrast-enhanced CT and MRI for identifying malignancy in kidney lesions in patients with impaired kidney function in view of the serious adverse effects associated with CT and MR contrast agents in this patient population.

#### 2.0 STUDY OBJECTIVES

#### 2.1 Primary Objective

To estimate the sensitivity and specificity of qualitative interpretations of CEUS in diagnosing kidney malignancy in patients with CKD and a suspicious or indeterminate lesion on non-contrasted imaging compared to the truth standard

described in 1.4 and 4.2.6.

#### 2.2 Secondary Objectives

To estimate the sensitivity and specificity of quantitative metrics generated from CEUS in diagnosing kidney malignancy in patients with CKD and a suspicious or indeterminate lesion on non-contrasted imaging compared to the truth standard described in 1.4 and 4.2.6. We will also compare sensitivity and specificity of quantitative metrics to the sensitivity and specificity of the qualitative interpretations.

#### **3.0 PATIENT ELIGIBILITY**

#### 3.1 Inclusion Criteria

To be eligible for the present study, patients must meet the following criteria:

**3.1.1** Able to provide written informed consent

- **3.1.2** Willing to comply with protocol requirements
- **3.1.3** At least 18 years of age

**3.1.4** Have kidney disease, defined as either CKD II-V, determined by estimated glomerular filtration rate (GFR) of <90 and derived from serum creatinine measurements, or albuminuria/proteinuria, determined by albumin to creatinine ratio or protein to creatinine ratio of >30mg/gm within 3 months of recruitment, or on dialysis or having received a kidney transplant or have biopsy proven kidney disease

**3.1.5** Have at least one kidney lesion identified but incompletely characterized on a non-contrasted US, CT, or MR exam for which the patient's provider recommends follow-up studies or further evaluation with an additional imaging tests.

#### 3.2 Exclusion Criteria

Patients who meet any of the following criteria will be excluded for enrollment:

**3.2.1** Critically ill or medically unstable and whose critical course during the observation period would be unpredictable (e.g., chronic obstructive pulmonary disease (COPD) requiring oxygen)

**3.2.2** Known hypersensitivity to sulfur hexafluoride or to any component of perflutren lipid (Definity®)

**3.2.3** Right to left shunt, severe pulmonary hypertension (Pulmonary artery pressure >90mmHg), or adult respiratory distress syndrome

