#### CONFIDENTIAL UNIVERSITY OF NORTH CAROLINA

**3.2.4** Active cardiac disease including any of the following:

- Severe congestive heart failure (class IV in accordance with the classification of the New York Heart Association)
- Unstable angina.
- Severe arrhythmia (i.e. ventricular tachycardia, flutter fibrillation; ventricular premature complexes occurring close to the preceding T-wave, multifocal complexes).
- Myocardial infarction within 14 days prior to the date of proposed Definity® administration.
- Uncontrolled systemic hypertension (systolic blood pressure (BP) >180 mm Hg and/or diastolic BP >100 mm Hg despite optimal medical management

**3.2.5** Is in an intensive care setting

**3.2.6** Has an unstable neurological disease (e.g cerebrovascular accident (including transient ischemic attacks (TIAs) within the 3 months before signing of informed consent

**3.2.7** Has undergone an invasive procedure on kidney lesion (e.g. tissue biopsy, surgery, nonsurgical cytoreductive procedure) since identification of lesion via US without contrast

**3.2.8** Has any other medical condition or other circumstances that would significantly decrease the chances of obtaining reliable data or of achieving the study objectives such as:

- Mental illness
- Drug abuse

**3.2.9** Female patient who is pregnant or lactating (the possibility of pregnancy has to be excluded by negative serum or urine B-HCG results, obtained within 24 hours before the perflutren lipid administration, or on the basis of patient history, e.g.: tubal ligation, hysterectomy or a minimum of 1 year without menses)

**3.2.10** Obesity that limits obtainment of acceptable images

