#### Serious Cardiopulmonary Reactions

Serious cardiopulmonary reactions including fatalities have occurred uncommonly during or shortly following perflutren-containing microsphere administration, typically within 30 minutes of administration. The risk for these reactions may be increased among patients with unstable cardiopulmonary conditions (acute myocardial infarction, acute coronary artery syndromes, worsening or unstable congestive heart failure, or serious ventricular arrhythmias). Always have cardiopulmonary resuscitation personnel and equipment readily available prior to perflutren administration and monitor all patients for acute reactions. The reported reactions include: fatal cardiac or respiratory arrest, shock, syncope, symptomatic arrhythmias (atrial fibrillation, tachycardia, bradycardia, supraventricular tachycardia, ventricular fibrillation, ventricular tachycardia), hypertension, hypotension, dyspnea, hypoxia, chest pain, respiratory distress, stridor, wheezing, loss of consciousness, and convulsions.

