#### Anaphylactoid Reactions

In postmarketing use, uncommon but serious anaphylactoid reactions were observed during or shortly following perflutren-containing microsphere administration including: shock, hypersensitivity, bronchospasm, throat tightness, angioedema, edema (pharyngeal, palatal, mouth, peripheral, localized), swelling (face, eye, lip, tongue, upper airway), facial hypoesthesia, rash, urticaria, pruritus, flushing, and erythema. These have occurred in patients with no prior exposure to perflutren-containing microsphere products.

Systemic Embolization of Perflutren in Patients with Cardiac Shunts In patients with right-to-left, bi-directional, or transient right-to-left cardiac shunts phospholipid-encapsulated microspheres can bypass the pulmonary particlefiltering mechanisms and directly enter the arterial circulation resulting in

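### Section 1.3.2 says any history of cardiac shunt is excluded, but criterion 3.2.3 covers only right-to-left shunt; unstable heart failure below class IV is named in no criterion

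*Combined protocol and SAP*

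**What the plan says.** The background makes a safety commitment. Section 1.3.2, Cardiopulmonary Reactions, says: "Patients with a history of cardiac shunts, pulmonary hypertension or unstable cardiopulmonary conditions will be excluded from our study". Just before this, the same section reports that cardiac shunts remained among the label contraindications after the 2008 review, again without giving a type.

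The enrolment criterion is narrower. Criterion 3.2.3 begins "Right to left shunt, severe pulmonary hypertension", sets the limit for the latter at a pulmonary artery pressure above 90 mmHg, and adds adult respiratory distress syndrome.

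Section 5.7, in its warning about systemic embolization, names the shunts of concern as "right-to-left, bi-directional, or transient right-to-left cardiac shunts". In its warning about serious cardiopulmonary reactions it lists four kinds of unstable condition: acute myocardial infarction, acute coronary syndromes, and "worsening or unstable congestive heart failure, or serious ventricular arrhythmias".

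Criterion 3.2.4 opens with "Active cardiac disease including any of the following" and gives five items. The heart failure item is "Severe congestive heart failure (class IV in accordance with the classification of the New York Heart Association"). Another is "Unstable angina"; the rest are severe arrhythmia, myocardial infarction in the preceding 14 days, and uncontrolled hypertension. Criterion 3.2.1 excludes patients who are critically ill or medically unstable with an unpredictable course, and 3.2.5 excludes those in intensive care.

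**The concern.** Section 4.1 makes 3.1 and 3.2 the enrolment gate, and under 4.2.2 two institutions apply it. Anyone who relies on 1.3.2 to judge the risk of the study, an IRB for example, is told that a group is kept out when the gate as written does not keep all of it out.

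The conflict also blurs what counts as a deviation. Section 9.4 requires the study to be run exactly as the approved protocol describes, and 9.4.2 requires approval to enrol someone who fails an eligibility criterion. A patient with a shunt that is not right-to-left passes 3.2, so 9.4.2 is not triggered, yet enrolling that patient contradicts 1.3.2. If such a patient had a reaction, the protocol would not settle whether the patient should have been dosed.

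**Working it through.** No figure in the plan depends on this point, so the check is a comparison of text.

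**Shunts**

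| Case | 1.3.2 | 3.2.3 | 5.7 embolization warning |
|---|---|---|---|
| Right-to-left | excluded | excluded | named |
| Transient right-to-left | excluded | not named; can be read as covered | named |
| Bi-directional | excluded | not named; can be read as covered, since it includes right-to-left flow | named |
| No right-to-left flow | excluded | not excluded | not named |
| Past shunt (history only) | excluded | history not mentioned | history not mentioned |

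The last two rows are the firm mismatch: 1.3.2 excludes, and no shunt criterion in 3.2 does. The second and third rows are a matter of clarity, because 3.2.3 does not limit itself to fixed or permanent shunts.

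No other step closes the gap. Section 6.1 requires a complete medical history but names no shunt item. Criterion 3.2.8 concerns conditions that threaten reliable data or the study objectives, so it is not a safety screen for shunts. The withdrawal grounds in 4.4 concern illness, adverse events, patient choice and changes in condition; a known, unchanged shunt is none of these.

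**Unstable cardiopulmonary conditions**

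Taking the four conditions in 5.7 in turn:

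1. Acute myocardial infarction: matched in 3.2.4 by infarction within 14 days.
2. Acute coronary syndromes: matched in 3.2.4 by unstable angina and recent infarction.
3. Serious ventricular arrhythmias: matched in 3.2.4 by severe arrhythmia.
4. Worsening or unstable heart failure: matched by name only at NYHA class IV. Below class IV, exclusion depends on someone judging the patient medically unstable under 3.2.1, or reading the condition into the open lead-in of 3.2.4. Criterion 3.2.5 applies only if the patient is in intensive care.

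Three of the four conditions therefore have a direct counterpart, and the fourth has a partial one.

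**The case against.** The best reply is that 4.1 gives staff one operative list, so a broader sentence in the background does no harm. It is true that the list can be applied without hesitation. That does not remove the contradiction, because 1.3.2 is worded as a commitment about who will be excluded from this study.

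A second reply is that the danger set out in 5.7 does not clearly reach the patients let in. This stands. A reader might infer that the gate admits patients to the embolization hazard. But 5.7 ties microspheres entering the arterial circulation to right-to-left, bi-directional and transient right-to-left shunts, and all three can fairly be read into 3.2.3. The patients who are clearly not excluded have a shunt without right-to-left flow, or only a past shunt, and the documents do not attach that hazard to them.

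A third reply is that unstable patients are largely covered. This also stands. A reader might infer that 3.2.3 and 3.2.4 cover little beyond right-to-left shunt and class IV heart failure. They also name severe pulmonary hypertension, adult respiratory distress syndrome, unstable angina, severe arrhythmia, recent infarction and uncontrolled hypertension, and 3.2.1 and 3.2.5 add to these. Nor does the class IV limit show that lower classes are wrongly admitted: class grades severity, whereas 5.7 speaks of stability, and neither 1.3.2 nor 5.7 says that stable failure below class IV should be excluded.

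**Conclusion.** The point holds for shunts: 1.3.2 excludes any history of cardiac shunt, 3.2.3 excludes right-to-left shunt only, and a candidate with another or a past shunt is described as excluded yet passes the shunt criterion. The heart failure point is secondary: a wording gap that leaves unstable failure below class IV to judgement, not a proven omission.

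The number of patients affected cannot be derived, because the documents give no frequency for either condition among the 75 to be recruited. The accuracy estimates and sample size in section 8 do not depend on it. The conclusion assumes that the unqualified shunt wording in 1.3.2 is meant literally. If it was shorthand for 3.2.3, the remedy is still to align the two, in the other direction.

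The same pair of sentences also differs on pulmonary hypertension, which is unqualified in 1.3.2 but severe, with a pressure limit, in 3.2.3. That is a separate discrepancy and carries no weight here.

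**What to change.** Reconcile 1.3.2, 3.2.3, 3.2.4 and 5.7 so that the safety commitment and the enrolment criteria agree on three things: which shunt types are meant, whether a history or only a current shunt counts, and which unstable cardiopulmonary conditions are meant, including how heart failure below class IV is treated. Say explicitly whether bi-directional and transient right-to-left shunts fall within 3.2.3. Carry the agreed list into the history taken under 6.1, so that both sites ask the same questions. The clinical investigators must decide which wording is right; this review takes no position on it.

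The cost is protocol wording and an IRB amendment. If the stricter wording is chosen, a few candidates may become ineligible. The analysis plan does not change.
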